Overview of study approach. In a 24 week RCT based in a large urban area with high rates of OUD and HIV, we will recruit 250 out-of-treatment opioid users from SEPs and randomize 1:1 to onsite BMT initiation (**O-BMT**) or enhanced referral. Over two weeks, participants in the O-BMT arm will see a buprenorphine provider twice, receive prescriptions of medication, and then their care will be transferred to a community health center (CHC) for maintenance BMT. In the control arm, participants will receive enhanced referral to a CHC for initiation and maintenance BMT. We will assess participants with urine drug tests, questionnaires, and medical record review studying treatment engagement, treatment outcomes (opioid use, HIV risk behaviors) and programmatic service utilization in order to establish effectiveness and costs. We will also assess buprenorphine diversion using electronic monitors, urine drug testing, and sequential surveys.

Setting. A. New York Harm Reduction Educators (NYRHE) is the largest harm reduction agency in New York City with over 35 staff members and serving over 5000 clients annually. At two community-based offices and 11 street-side locations, NYHRE provides participants with syringe exchange; referral for medical, dental and addiction treatment; and other supportive services. The majority of NYHRE's clients are Hispanic or black, male, 40-49 years old, and PWID. Diverse staff members (case managers, outreach workers, and syringe exchange staff) have received training on BMT. O-BMT will be offered at community-based offices only.

B. Washington Heights CORNER Project (WHCP) is another harm reduction agency situated in an area highly affected by OUD and HIV. At its community-based office, WHCP provides clients with syringe exchange; referrals for medical, dental, or addiction treatment; and other supportive services. WHCP serves over 1500 clients annually with similar characteristics as NYHRE. WHCP staff members have received training on BMT.

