RBS = HIV Risk Behavior Survey; CES-D = Center for Epidemiologic Studies Depression Scale; DTCQ-8 = Drug-Taking Confidence Questionnaire, 8 item version; EQ-5D = EuroQol 5D-5L; PCBSS = Primary Care Buprenorphine Satisfaction Scale; SOCRATES = The Stages of Change Readiness and Treatment Eagerness Scale

Questionnaires: Using the survey feature on REDcap which plays an audio recording of questions as it displays the question on a computer screen, will be used by the RA to administer questionnaires. Interviews will assess for sociodemographic information, motivation for treatment, HIV risk behaviors, buprenorphine diversion, and other variables (see below). Interviews will last 45-60 minutes.

Electronic medication adherence monitors: Wisepill electronic monitors will be used allowing us to monitor if and when medication is taken. Participants will receive a prescription for buprenorphine. After receiving the prescription, research staff will supervise the patient as they place their medication into the Wisepill Medication adherence monitors. Each time the device is opened it sends a signal to a password protected database.

Fidelity of referral: The SEP staff will follow identical procedures for referral or transfer of care to a CHC. We will not be able to blind participants or staff to study allocation. Therefore, we will record the number of appointments and reminder phone calls performed in each arm to ensure that SEP staff members are not providing differential effort in facilitating referral to a CHC.

Main outcome variables: *Aim 1: Primary outcome (efficacy):* we will use a dichotomous measure (yes/no) of **BMT engagement** defined as having an active buprenorphine prescription at 30 days after randomization.³⁰ Secondary outcome measures assessed at 24 weeks will include: proportion who filled a prescription for BMT, total weeks prescribed BMT, and time to BMT initiation (all continuous measures).

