D.10 Power analysis. To estimate the effect size for the O-BMT intervention, we drew from prior pilots of onsite treatment. Stancliff et al.⁴² offered BMT to SEP participants (N = 100) and 68% were engaged in BMT at 3 months (30 day engagement was not reported). Tringale et al.⁴³ offered BMT to SEP participants (N=9) over 15 days and then transferred care to treatment program. Following onsite initiation, 33% ultimately engaged in BMT. Daniels et al.⁸⁰ offered BMT at a community-based recovery center (N = 78) and 49% were transitioned to primary care site to continue treatment. For enhanced referral, we estimated rates of engagement in BMT

Principal Investigator: [name]

Table 3. Sample size calculation for hypothesized BMT engagement rates			
Enhanced referral arm	O-BMT arm		
	33%	49%	68%
	0%	40	26
	9%	80	36
	16%	200	62

Note: Sample sizes determined based on Fisher exact test when engagement rate in referral arm is 0.1%. For other tests, the sample sizes were determined based on Chi-square tests.

14%. Though this is larger than tolerable margins for non-inferiority, we will have good estimates of the frequency of diversion in the O-BMT arm, which will provide important safety data for onsite treatment.

For Aim 3, assumptions are based on differences in cost and effect, standard deviations of cost and effect, the correlation of the difference in cost and effect, desired confidence and power levels, and the maximum willingness-to-pay value.^{106,107} We estimated the power for the primary outcomes of our economic analysis (cost-per QALY and cost-per abstinent year) using the target sample size of 250 (125 per group), and a range of values for the aforementioned assumptions, based on prior economic evaluations of substance use disorder interventions. We estimate at least 90% power to be 95% confident that an intervention is acceptable at the commonly cited willingness-to-pay threshold of \$100,000 per QALY.⁹⁵

PROTECTION OF HUMAN SUBJECTS

Human subjects involvement and characteristics: We will enroll 250 participants from syringe exchange programs (SEPs) with opioid use disorder (OUD) who are interested in buprenorphine maintenance treatment (BMT) and are motivated for treatment.

Eligibility criteria include:

- 1) age \geq 18 years
- 2) opioid use disorder by DSM-V criteria
- 3) interest in BMT
- 4) motivation for OUD treatment, based on SOCRATES
- 5) willingness to accept CHC referral

Exclusion criteria include:

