- 1) receiving opioid agonist treatment in the past 30 days (confirmed by NY Prescription Drug Monitoring Program);
- 2) inability to provide informed consent
- 3) unstable mental illness (e.g., suicidality, psychosis, etc.)
- 4) severe alcohol use disorder or benzodiazepine use disorder by DSM-V criteria
- 5) hypersensitivity to buprenorphine or naloxone.
- 6) pregnancy (confirmed via urine testing)

Rationale for inclusion/exclusion criteria: Study participants will include out-of-treatment SEP participants with OUD. We will only include participants who are interested in BMT, motivated for OUD treatment, and willing to accept referral to a CHC for treatment, because our goal is to increase engagement in comprehensive BMT. Providing BMT onsite at SEPs could attract participants who are unready to stop illicit opioid use and only want buprenorphine temporarily to reduce withdrawal symptoms or because they do not have access to their illicit opioid of choice. There may be benefits to this type of symptom treatment, but our study is not designed to evaluate these benefits. We will exclude those with clinical contraindications to BMT,

from our own pilot data and several studies that referred SEP participants to MMT. Engagement after passive referral may be as low as 0%,¹⁴ while referral to MMT has resulted in 9-16% of SEP participants engaging in treatment.³⁷⁻³⁹ Therefore, we will recruit a sample of 250, which allowing for up to 20% attrition (n=200), giving us at least 80% power for the primary outcome (**BMT engagement**) in all proposed scenario.

For Aim 2, we chose the intention to treat analysis as the primary outcome. With a sample size of 250 and an expect rate of diversion of 10-25%, we will only have 80% power to declare that diversion rate in the O-BMT arm is non-inferior to the referral arm if the inferiority margin of the risk difference is 10-

Principal Investigator: [name]

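### Time to BMT initiation is classed as a continuous measure, with no rule for participants who never initiate

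*Combined protocol and SAP*

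**What the plan says.** Follow-up lasts 24 weeks. On size and allocation, the overview of the study approach states: "we will recruit 250 out-of-treatment opioid users from SEPs and randomize 1:1". That is 125 per arm.

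Under Main outcome variables, Aim 1, the primary outcome is an active buprenorphine prescription at 30 days. The text goes on: "Secondary outcome measures assessed at 24 weeks will include: proportion who filled a prescription for BMT", then "total weeks prescribed BMT, and time to BMT initiation (all continuous measures". The section does not say what event marks initiation, when the clock starts, or what is recorded for someone who never starts.

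The Analysis section gives a chi-square test and a logistic model for 30-day engagement, and generalized estimating equations for opioid use (H2) and injecting risk (H3). It names no test or model for time to initiation. Primary analyses are intention to treat, with secondary per-protocol analyses among those who actually start BMT. The Missing data paragraph provides multiple imputation for categorical data only. No survival or censoring method appears anywhere in the document.

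Section D.10 (Power analysis) gives engagement rates, not initiation rates. For referral: "Engagement after passive referral may be as low as 0" per cent, while "referral to MMT has resulted in 9-16% of SEP participants engaging in treatment". For onsite treatment the inputs are 68% engaged at 3 months, "49% were transitioned to primary care site to continue treatment", and "Following onsite initiation, 33% ultimately engaged in BMT".

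**The concern.** A time to initiation exists only for people who initiate. If it is analysed as its stated type, the analyst must do one of two things:

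- Compare means among initiators. That conditions on an event after randomisation which the intervention is designed to change, so the two groups compared are no longer the randomised groups.
- Give non-initiators a number. The estimate then depends on that number, and the plan states none.

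The choice would be made after the data are seen. At stake is one of the more direct secondary measures of what onsite treatment should do, namely get people started and started sooner. An initiators-only mean discards the first part of that effect.

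**Working it through.** **1. The plan's own figure.** The documents give no figure for time to initiation. The nearest is the primary sample size at 16% vs 33%. Taking two-sided alpha 0.05 (not stated for this test, so assumed), 80% power and pooled variance:

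n per arm = [1.96·√(2 × 0.245 × 0.755) + 0.8416·√(0.16 × 0.84 + 0.33 × 0.67)]² / 0.17² = (1.192 + 0.502)² / 0.0289 ≈ 99.3, rounded up to 100.

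The total is 200, and 200 / 0.80 = 250. Both figures reproduce, and nothing below changes them.

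**2. How many controls would have a time.** Assume that 24-week initiation under referral equals the planned engagement rates: 0 × 125 = 0, 0.09 × 125 ≈ 11, 0.16 × 125 = 20. At the ceiling, 105 of 125 would have no value. At 0%, an initiators-only comparison could not be computed. If initiation were twice the ceiling (32%, assumed), 0.68 × 125 = 85 would still have none.

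**3. What an initiators-only mean can show.** Assume initiation of 16% (control) and 33% (O-BMT) by day 168. This pair is for illustration only, and 33% is not an initiation rate in the plan. The timing shapes are also assumed. Restricted mean time to day 168 = p × (mean time among initiators) + (1 − p) × 168.

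- *A. Starts spread evenly over days 0–30 in both arms.* Initiators-only difference: 15 − 15 = 0 days. Restricted means: control 0.16 × 15 + 0.84 × 168 = 143.5; O-BMT 0.33 × 15 + 0.67 × 168 = 117.5; difference −26.0 days.
- *C. Control starts over days 0–14, O-BMT starts over days 0–30.* Initiators-only difference: 15 − 7 = +8 days, so O-BMT looks slower. Restricted means: control 0.16 × 7 + 0.84 × 168 = 142.2; O-BMT 117.5; difference −24.7 days, so O-BMT is faster.

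A simulation (600 runs, 125 per arm) compared an initiators-only t-test with a log-rank test in everyone, and added B, constant hazards:

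| Timing | Initiators-only difference, O-BMT minus control (days) | t-test rejects | Log-rank power |
|---|---|---|---|
| A | 0.0 | 4.7% | 0.88 |
| B | −3.4 | 6.2% | 0.88 |
| C | +8.0 | 99.8% | 0.82 |

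In A and C the expected initiators-only difference does not involve the initiation probabilities at all. With O-BMT initiation raised to 68%, it stays at 0.1 and 8.0 days, while the restricted mean differences grow to −79.7 and −78.5 days.

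**4. Inserting a value.** In A, giving every non-initiator the value c produces a difference of 0.17 × (15 − c) days. At c = 168 this is −26.0. The size is set by c, which is why c must be stated in advance.

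**5. Events for a time-to-event analysis.** At 16% vs 33%, expected events are 125 × 0.49 ≈ 61. Under constant hazards the hazard ratio is ln(0.67) / ln(0.84) = 2.30. Schoenfeld power is Φ(√(61.25 / 4) × ln 2.30 − 1.96) ≈ 0.90.

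**The case against.** The strongest reply is that this is an unspecified analysis, not a wrong one. That is largely right, and it limits the point in several ways.

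- A reader might infer that the plan drops non-initiators and is therefore biased. The documents do not say so. A 24-week cap, or censoring, fits the text equally well, since the outcome is assessed at 24 weeks. The word continuous is also weak evidence of method: the same label covers a proportion here, and the illicit opioid use paragraph applies it to a percentage abstinent.
- A reader might infer that most controls are expected never to start. The 0% comes from passive referral and the 9–16% from referral to methadone treatment. The control arm is enhanced referral, with an appointment within one week and a reminder call, in people selected for motivation. No 24-week initiation rate is given.
- A reader might subtract the onsite rates from 100% and conclude that 32–67% of the O-BMT arm would lack a time. That is unsupported, because those rates are measured after initiation. In the pilot behind the 33%, 7 of 9 participants completed the onsite protocol (Background), so at least that many had started.
- A reader might infer a fixed direction of bias. In A and B the initiators-only test is merely uninformative. The reversal in C needs a timing pattern that the documents do not predict.

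The reply also notes that none of H1–H5 tests this outcome, and that the filled-prescription proportion would still show non-initiation by arm. Both are true, and they limit the consequence. They do not settle how time to initiation is to be analysed. For diversion (H4), the plan recognises the same difficulty with people never prescribed and expressly keeps intention to treat. Time to initiation has no such statement.

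**Conclusion.** The point holds as a misclassified and incompletely specified secondary outcome. The stated type does not fit a variable that is undefined for non-initiators, and no censoring rule, survival method or assigned value is given. An initiators-only comparison could hide a real difference or distort it, and which of these happens depends on when people start.

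The size is illustrative. About 20 of 125 controls would contribute a time if initiation under referral matched the 16% engagement ceiling, and more would if enhanced referral does better. No corresponding count can be given for O-BMT. The simulated results rest on assumed initiation rates and timing. The primary 30-day analysis and the sample of 250 are unaffected.

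**What to change.** Reclassify the three measures in the outcome section and add their analyses under Aim 1:

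- **Time to initiation:** time-to-event, from randomisation to first filled buprenorphine prescription, in all randomised participants, censored at 24 weeks. Report Kaplan-Meier curves by arm and a log-rank or Cox comparison stratified by site, the randomisation stratum. A restricted mean to 24 weeks would also be acceptable if it is named in advance.
- **Ever filled a prescription by 24 weeks:** binary, in all randomised participants.
- **Total weeks prescribed:** state that participants who never initiate count as 0.

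Any description of timing among initiators should be labelled as descriptive and not used to compare the arms.

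The cost is wording only. Fill dates are already to be collected from the state prescription monitoring program (Medical Records), so no new data, visits or participants are needed.

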Figure 2: Study arms

Maintenance. After two onsite visits with the study provider, BMT will be transferred to a CHC via enhanced referral. The CHC will guarantee access to a BMT provider within one week (see Letters of Support) and research staff will assist with scheduling appointments. Physicians at the CHC are experienced treating OUD and will provide standard BMT (weekly visits at initiation, change to monthly visits with clinical stability, urine drug testing, psychosocial counseling) according to a written protocol (see appendix 1.). Participants will receive reminder calls the day before their appointment.

Risk mitigation strategy for participants who take sedatives: Clinical decisions regarding BMT dosing, treatment continuation, and referral for additional psychosocial treatments will be based on the clinical judgement of BMT providers (i.e., buprenorphine-waivered physicians). Consistent with FDA-guidance,

Principal Investigator: [name]

physicians will provide the following aspects of care to participants who are taking benzodiazepines or other sedatives (including alcohol):

- Education about the serious risks of combined use, including overdose and death, that can occur with CNS depressants even when used as prescribed, as well as when used illicitly.
- Developing strategies to manage the use of prescribed or illicit benzodiazepines or other CNS depressants when starting BMT.
- Tapering the benzodiazepine or CNS depressant to discontinuation if possible.
- Verifying the diagnosis if a patient is receiving prescribed benzodiazepines or other CNS depressants for anxiety or insomnia, and considering other treatment options for these conditions.
- Recognizing that patients may require BMT indefinitely and their use should continue for as long as patients are benefiting and their use contributes to the intended treatment goals.
- Coordinating care to ensure other prescribers are aware of the patient's buprenorphine treatment.
- Monitoring for illicit drug use, including urine screening

If the risks of BMT outweigh the clinical benefits, participants will be referred to an opioid treatment program for care and treatment.¹⁰⁸

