Medical Records: We will extract medical record data from the CHC, including prescription and visit information to assess *treatment engagement* and *retention in care*. Prescription data will include information both from the electronic medical record (prescriptions) and the NY Prescription Drug Monitoring Program (medications dispensed). As mandated by law, the later source includes all controlled substances dispensed by all pharmacies in New York State. Prescription data will include medication name, strength, directions, number of pills, number of refills, date of prescription, prescriber, and date medication was filled. Visit data will include date of visit, and provider. If participants request referral to a different site for BMT or are transferred to an alternative form of OUD treatment (e.g., methadone maintenance), we will request medical records using the signed, HIPAA-compliant release for medical records.

Urine Drug Testing: All research visits will include urine collection, which will be tested for buprenorphine, opiates, oxycodone, methadone, cocaine, methamphetamine and benzodiazepines.

Table 2. Timing and delivery of intervention and study measures

Measure	Study Instrument	Assessment Period (week)									
		0	1	2	4	6	8	1	2	2	4
Urine Drug Tests											
Opioid use	Urine Drug Testing	x	x	x	x	x	x	x	x	x	x
Questionnaires											
Sociodemographic information	BHIVES Study ⁶⁶	x									
HIV Risk Behaviors	RBS ⁸⁶	x		x					x	x	
Self-reported drug use	Addiction Severity Index ⁸⁷	x			x		x	x	x	x	
Depressive Symptoms	CES-D ⁸⁸	x		x				x	x	x	
Self-efficacy	DTCQ-8 ⁸⁹	x		x				x	x	x	
Quality of Life	EQ-5D ⁹⁰	x		x	x		x	x	x	x	
Patient satisfaction	PCBSS ⁹¹			x				x			

Principal Investigator: [name]

Motivation for treatment	SOCRATES ⁷³	X		X				X	
Stigma and Discrimination	Ahern et al. ⁹²	X						X	X
Buprenorphine Diversion	MGH Medication Questionnaire			X	X		X	X	X
Non-study resource utilization	Non-Study Resources Form	X			X		X	X	
Criminal justice resource utilization	Criminal and Legal Activities Form	X			X		X	X	
PTSD symptoms	PCL-5				X		X	X	X
Traumatic reexposure	LEC-5				X		X	X	X
Medical Record Review									
Treatment engagement	-					30 days			
Retention in care	-					3 month, 6 month			

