Aim 1: Secondary outcomes (efficacy): a.) Illicit opioid use: We will check urine drug testing at each research visit and use the Addiction Severity Index (ASI) to assess self-reported substance use.⁸⁷ We have adapted the ASI to also assess use of illicit buprenorphine.¹³ We will report the following continuous measures in each study arm: the percentage of urine drug tests that are positive for illicit opioids (opiates, oxycodone, methadone, illicit buprenorphine), self-reported days of illicit opioid use, and percent of participants achieving *opioid abstinence*, defined as no illicit opioid use based on self-report and urine drug testing.

Principal Investigator: [name]

b.) Retention in treatment: For participants initiating BMT, we will determine whether they are retained in treatment at three and six months following initiation (dichotomous measure). We will define retention as having a medical visit and active buprenorphine prescription each month after BMT initiation. We will also determine the proportion of days following BMT initiation that participants had an active prescription in order to detect lapses in treatment (continuous measure).

c.) HIV risk behaviors: We will determine changes in drug-related HIV risks using the HIV Risk Behavior Survey – a validated, well-studied instrument that documents injection and sexual behaviors over the previous 30 days. This instrument has been studied among out-of-treatment PWID and BMT patients.^{86,93} As previously reported, we will create a dichotomous measure (yes/no) of injecting risk based on self-report of at least one risk behavior (sharing syringes, not using bleach to clean syringes, sharing cookers, or front/back loading of syringes).⁹³ Individual risk behaviors will be explored individually.

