Aim 2: Primary outcome (safety): We will use a dichotomous measure (yes/no) of **buprenorphine diversion** for all participants to determine how many sell or give away prescribed medication. We will define diversion as having at least one problem behavior over the 24 weeks: non-adherence to prescribed medication on electronic monitoring, self-reported diversion, or a urine sample consistent with diversion. Adherence will be determined weekly with Wisepill adherence for one week equaling $X/7Y$, where X = number of openings in one week and Y = number of doses prescribed per day. For the composite measure, non-adherence will be considered < 90% adherence. We will adapt the MGH Medication Questionnaire, which assesses misuse of prescribed medications, including selling medication, letting others take prescribed medication, or taking medication to get “high”. For the composite measure, self-reported diversion will be defined as an affirmative response to the question, “In the past 2 weeks, have you sold your buprenorphine to others?” We will also test each urine sample for buprenorphine, and if absent among participants prescribed BMT, the urine sample will be considered consistent with diversion. Each behavior will also be explored individually.

Aim 2: Secondary outcomes (safety): We will also report illicit buprenorphine use (i.e., buprenorphine detected in urine samples of participants who are not prescribed BMT), and determine changes in illicit buprenorphine use from baseline to study completion among participants in each study arm.

Aim 3: Primary outcome (incremental cost-effectiveness ratio, ICER): The ICER will be calculated by dividing the incremental mean cost of the O-BMT arm relative to the control arm by the incremental mean effectiveness of the O-BMT arm relative to the control arm (instruments used to measure costs and effectiveness are described in detail below). The primary economic effectiveness outcome will be the quality-adjusted life-year (QALY), a measure that incorporates both duration and health-related quality-of-life and is recommended as the primary economic effectiveness measure.⁹⁴ The QALY captures a wider range of consequences than other clinical effectiveness measures, and permits comparisons across disorders and interventions, allowing for broader economic interpretation. Also, generally accepted value thresholds have been established for QALYs, but not for clinical measures.⁹⁵

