Appendix 1.

CHCC BUPRENORPHINE MAINTENANCE TREATMENT (BMT) PROTOCOL

1. Intake

- a. On the first visit, gather the H&P w attention to the substance use history, set expectations, check LFTs and utox
- b. Use smart phrase to gather complete substance use history
- c. Use smart phrase to generate BMT Patient Agreement

2. Induction

- a. Second visit, the patient will receive Bupe induction instructions and COW scale.
 - i. Tips: Start with 8 mg tabs/films and ask patient to break in 1/2 or even 1/4. Also prescribe clonidine, loperamide, and ibuprofen for withdrawal symptoms.
 - ii. Induction can be done at home or in the office
 1. Home induction has been tolerated and successful at CHCC

3. Induction and Stabilization

- a. See the patient for follow-up in 1 week, then again 1-2 weeks later until the patient is on a stable dose
- b. Doses can be adjusted based on symptoms of withdrawal and cravings. Sometimes this can be challenging as anxiety can mimic withdrawal symptoms.
- c. Total daily dose: The usual dose is 16 mg total daily (the vast majority range between 8-24mg daily) and doses can be increased by 4 mg/day.
- d. Frequency: Can be dosed daily or bid, adjust according to symptoms, often pts like to split their doses, which is fine

4. Maintenance

- a. Once dose is stable, can space out visits to monthly
- b. Check urine drug testing at every follow-up visit
- c. Assess for use of other substances (cocaine, alcohol, benzodiazepines, etc.) at each follow-up visit
- d. Adopt an uniform approach about cocaine, alcohol, or benzodiazepine use
 - i. Refer to social worker for psychosocial counseling
 - ii. Counsel all patients to minimize use of alcohol, benzodiazepines, and other sedatives
 - iii. Refer to an opioid treatment program if polysubstance use makes risks of continuing buprenorphine treatment greater than benefits

5. Discharge from Treatment

- a. If patients are hostile to staff or adulterate urine they will be given an administrative warning. These expectations should be made clear from day 1.
- b. Repeat offenders should be discharged from the practice and referred to an opioid treatment program

6. Lost to Follow Up:

- a. Track patients who have ever been evaluated for Bupe at your clinic, and periodically review with program coordinator and community outreach worker about outreach/retention efforts for loss to follow up patients.

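### The urine outcome lists methadone as an illicit opioid with no exception for treatment methadone, although the plan foresees some participants moving to methadone treatment

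*Combined protocol and SAP*

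**What the plan says.** **Outcome definition.** In the protocol, Aim 1: Secondary outcomes (efficacy), item a, one reported measure is "the percentage of urine drug tests that are positive for illicit opioids (opiates, oxycodone, methadone, illicit buprenorphine". The same item defines opioid abstinence as follows: "defined as no illicit opioid use based on self-report and urine drug testing".

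**Buprenorphine rule.** Aim 2: Secondary outcomes (safety) explains illicit buprenorphine use by prescription status: "buprenorphine detected in urine samples of participants who are not prescribed BMT". There is no matching sentence for methadone.

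**Methadone treatment during follow-up.** The Medical Records paragraph covers participants who "are transferred to an alternative form of OUD treatment (e.g., methadone maintenance), we will request medical records". It gives assessment of engagement and retention as the purpose of the health center record extract. It does not say that any record will be used to classify a urine result. The risk mitigation strategy for participants who take sedatives says that, when BMT is judged to carry more risk than benefit, "participants will be referred to an opioid treatment program for care and treatment". Appendix 1, under Maintenance, has a similar instruction: "Refer to an opioid treatment program if polysubstance use makes risks of continuing buprenorphine treatment greater than benefits".

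**Analysis.** H2 compares urine results between arms by generalized estimating equations (GEE) at weeks 1, 2, 4, 6, 8, 12 and 24. A second H2 model uses self-reported days of use. Primary analyses are by intention to treat.

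**The concern.** The trial tests urine for two drugs that are also agonist treatments for opioid use disorder. For buprenorphine the plan separates prescribed from illicit use. For methadone it does not, so a participant who leaves BMT for methadone maintenance and takes only that would, on the wording, count as using illicitly at each later visit and as not abstinent.

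Recent agonist treatment is an exclusion at entry, so the problem arises after randomization. Intention to treat keeps these participants in the comparison. At stake are the urine half of H2 and the abstinence outcome: illicit use would be overstated in any arm with transfers, and the arm with more transfers would look worse. Two analysts could also score the same sample differently, one by the list of analytes and the other by the word illicit.

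**Working it through.** The plan gives no rate, power or sample size for the urine outcome, so there is no figure to reproduce. The check is a comparison of definitions, followed by an illustration of size.

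**Definitions side by side**

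| Analyte | Marked illicit within the list? | Rule for prescribed drug? | Treatment use foreseen? |
|---|---|---|---|
| Buprenorphine | Yes | Yes (Aim 2 secondary outcomes) | Yes, both arms |
| Methadone | No | No | Yes (Medical Records); possibly through opioid treatment program referral |

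**What the definition reaches**

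- H2 urine model: yes, assuming that it takes its outcome from item a. The H2 text says only that urine results are used.
- Opioid abstinence: yes, because it relies on urine as well as self-report.
- H2 self-reported-days model: no.
- Primary outcome (buprenorphine prescription active at 30 days): no.
- Abstinent-year ICER: not shown. The Aim 3 text models days abstinent but does not say that they come from urine results.

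**Illustration of size**

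Inputs:
- Follow-up urines: 7 (H2). A participant on methadone from week 4 has 5 of them on treatment (weeks 4, 6, 8, 12, 24).
- d, the between-arm difference in the share transferred by week 4: not in the documents; assumed 0.05 to 0.10.
- q, the share of those participants' on-methadone urines with no other listed opioid: not in the documents; assumed 0.30 to 0.70.

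Formula: shift in the between-arm difference in percent positive = d × (5/7) × q, with the seven visits weighted equally, all urines collected, and q and transfer timing the same in both arms.

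- d = 0: shift = 0. Percent positive is still inflated within each arm. If 10% of each arm transfers, each is inflated by 0.10 × 5/7 × 0.30 = 2.1 points to 0.10 × 5/7 × 0.70 = 5.0 points.
- d = 0.05: 0.05 × 5/7 × 0.30 = 0.011 and 0.05 × 5/7 × 0.70 = 0.025, or 1.1 to 2.5 points.
- d = 0.10: 0.10 × 5/7 × 0.30 = 0.021 and 0.10 × 5/7 × 0.70 = 0.050, or 2.1 to 5.0 points.
- Ceiling for transfer at week 4, with q = 1: 0.05 × 5/7 = 0.036 and 0.10 × 5/7 = 0.071, or 3.6 to 7.1 points.
- Later transfer shrinks the shift. From week 12 only 2 of 7 urines are affected: 0.05 × 2/7 × 0.30 = 0.004 to 0.10 × 2/7 × 0.70 = 0.020, or 0.4 to 2.0 points.

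These are shifts in average percent positive, not in a GEE coefficient. The 9-16% in the power section is treatment engagement after referral to methadone in other syringe-exchange studies. It is not a transfer rate for this trial and is not used here.

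**The case against.** The strongest reply is that the list stands under the general term illicit opioids and that methadone taken as treatment is not illicit in ordinary usage. The extra qualifier on buprenorphine then has a simple explanation: it is the study drug, prescribed in both arms. That reading is possible, and the authors may have intended it. It does not remove the problem, because nothing says how a methadone-positive sample would be judged licit, while buprenorphine has both the qualifier and a rule.

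Second, the transfer provisions are contingencies, and the program referrals do not name methadone. Participants also had to be interested in BMT. This is fair: the number affected may be small. But the Medical Records paragraph does name methadone maintenance.

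Third, a reader might infer that transfer will probably differ by arm because the intervention changes access to buprenorphine. The documents do not support that. Both arms are meant to receive the same initiation procedures and identical referral procedures, and Appendix 1 governs health center care for both. Equal transfer is not assured, but neither a difference nor its direction is shown.

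Fourth, a reader might want the same exemption for prescribed opiates and oxycodone. That should not follow. Opiates are tested as a class, and a prescription on file cannot show that a positive test came from the prescribed drug. In this population the exemption could relabel illicit use as abstinence.

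**Conclusion.** The point stands as a gap in the definition of a secondary outcome. As worded, treatment methadone is scored as illicit use in the urine measure and in urine-based abstinence. The primary outcome and the self-reported-days model are not touched.

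The effect on the treatment comparison is unknown in size and sign. It is near zero with equal transfer, and about 1 to 5 points if transfer by week 4 differs by 5 to 10 points and 30-70% of the affected urines are otherwise clean. Every transfer and clean-urine input is an assumption.

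Two stronger readings should be resisted. The 3.6 to 7.1 points are a ceiling that treats every affected urine as free of other listed opioids, not an estimate. A reader might also conclude that the cost per abstinent year is biased; that is possible, but the plan does not tie days abstinent to urine results.

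**What to change.** Amend item a of the Aim 1 secondary outcomes before analysis:

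1. Count a methadone-positive urine as illicit only when treatment records show no methadone treatment covering the collection date. A sample positive for another listed illicit opioid remains positive.
2. Use treatment program records as the main source, supplemented by the Prescription Drug Monitoring Program. The protocol describes the latter as covering pharmacy dispensing, so it cannot be relied on alone for methadone given by a program.
3. Apply the same rule to urine-based abstinence.
4. State how unobtainable records are handled, for example by counting the sample as illicit in the main analysis.
5. Report the number in methadone treatment by arm, and repeat the urine and abstinence analyses under the current definition as a sensitivity analysis.
6. Leave the rule for opiates and oxycodone as it is.

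The cost is small: a change of wording and one added sensitivity analysis. The records are already to be requested under a signed release. The weakness is dependence on outside programs supplying them, which is why item 4 is needed. No new data collection and no change to clinical care are involved.
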